from the first day of study treatment through the end of study. Safety data will include local and systemic signs and symptoms, laboratory measures of safety/toxicity, and all adverse and serious adverse events.

Other Endpoints:

1. Change in the frequency of HIV infection per million resting CD4⁺ T cells (RCI) from baseline to post-treatment with VRC07-523LS combined with VOR.
2. Change in HIV RNA expression within resting CD4⁺ T cells in HIV-infected participants on stable ART from baseline to after the receipt of two series of VRC07-523LS given with VOR.
3. Change in HIV-1 RNA by low level viremia assay from baseline to post-treatment with VRC07-523LS and VOR.
4. Change in the chromosomally integrated viral reservoir as measured by quantitative-polymerase chain reaction (Q-PCR) from baseline to post-treatment with VRC07-523LS and VOR.
5. Change in frequency of viral envelope sequences detected in plasma or cells that are not recognized by VRC07-523LS from baseline to post-treatment with VRC07-523LS and VOR.
6. Pharmacokinetics of VRC07-523LS in combination with VOR.

Population: Healthy men and women of any race with HIV-1 infection, ages 18 through 64, suppressed on ART therapy for ≥ 24 months.

Phase: Phase I

Description of Sites/Facilities Enrolling Participants: This study will be conducted at a single site, The University of North Carolina (UNC) at Chapel Hill (USA). The study will enroll up to 12 participants.

Description of Study Intervention: Participants will receive two treatment interventions (series):

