3 OBJECTIVES AND ENDPOINTS

OBJECTIVES	ENDPOINTS	JUSTIFICATION FOR ENDPOINTS
Primary		
To evaluate the safety and tolerability of combination therapy with VRC07-523LS and VOR in HIV-infected participants on ART.	
Safety Occurrence of at least one \geq Grade 3 adverse event including signs/symptoms, lab toxicities, and/or clinical events that is possibly, probably, or definitely related to VOR or VRC07-523LS any time from the first day of study treatment through Step 4.
 
Safety data will include local and systemic signs and symptoms, laboratory measures of safety/toxicity, and all AEs and SAEs. Safety data will be routinely collected throughout the duration of the study.
	The study will use standard safety grades used in HIV clinical trials. Should these grades be exceeded, it is currently felt that such risks would be unacceptable in a research study of this nature.
Tertiary/Exploratory		

 1. Explore the effect of two cycles of VRC07-523LS and VOR on the frequency of latent, resting CD4+ T cell infection. 2. Compare HIV RNA expression within resting CD4+ cells in HIV-infected participants on stable ART before and after VRC07-523LS given with VOR at leukapheresis #1 (Step 1) and leukapheresis #2 (Step 4). 3. Explore the influence of VOR given with VRC07-523LS on low-level plasma 	
 1. Change in QVOA from resting CD4+ cells in HIV-infected participants on stable ART before and after VRC07-523LS given with VOR from baseline to post-VRC07-523LS/VOR. 2. Change in HIV RNA expression within resting CD4+ cells in HIV-infected participants on stable ART before and after VRC07-523LS given with VOR from baseline to post-VRC07-523LS/VOR. 3. Change in HIV-1 RNA by SCA from baseline to post-VRC07-523LS/VOR. 	These various measures of persistent HIV infection will allow us to detect an effect of VOR and VRC07-523LS (if any), validate expected exposures to these agents, and seek evidence of selective pressure exerted by VRC07-523LS on persistent HIV.

OBJECTIVES	ENDPOINTS	JUSTIFICATION FOR ENDPOINTS

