
viremia as measured by single copy assay (SCA) in participants who maintain suppression on ART.
 
4. Explore the impact of VOR and VRC07-523LS therapy on the quantity of integrated proviral DNA in T cell populations.
 
5. Characterize viral envelope sequences detected in plasma or cells that are not recognized by VRC07-523LS from baseline to post-VRC07-523LS/VOR.
 
6. Evaluate the pharmacokinetics of VRC07-523LS and VOR and determine whether anti-drug antibody (ADA) to VRC07-523LS can be detected in recipients administered VRC07-523LS in combination with VOR.
	
4. Change in the chromosomally integrated viral reservoir as measured by quantitative-polymerase chain reaction (Q-PCR) from baseline to post-VRC07-523LS/VOR.
 
5. Change in diversity of viral envelope sequences detected in plasma or cells that are not recognized by VRC07-523LS from baseline to post-VRC07-523LS/VOR.
 
6. Serum concentrations of VRC07-523LS in combination with VOR.
	

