QVOA measurements will be conducted with the leukapheresis samples collected prior to and following combined VOR/VRC07-523LS administration to determine if the frequency of resting CD4 T cell infection, expressed as IUPM, has declined. Since RCI frequency is a definitive measure of the minimum size of the HIV reservoir, a statistically significant decline in response to VRC07-523LS in combination with VOR treatment would be definitive evidence of a reduction in the HIV reservoir.

Plasma for Assays that measure low levels of RNA

Residual low-level viremia will be measured, as evidence suggests that such viremia originates in persistently infected cells, and low-level viremia might be reduced by an augmented antiviral immune response. Plasma for HIV-1 RNA will be obtained as required per the SOE in section 1.3 and stored for batched analyses. Two baseline sample determinations will be obtained during Steps 1 and 2 of the

protocol and 2-4 low level viremia assay measurements after combination therapy with VOR and VRC07-523LS will allow a robust evaluation of changes in plasma levels of cell-free HIV RNA.

Human Leukocyte Antigen (HLA) Typing

HLA testing will be performed at one time point in the study; however, if HLA type is already available in the medical record, it does not need to be repeated. The result will be used for research purposes.

Cytomegalovirus (CMV) IgG Testing

We will perform CMV testing for research purposes only at baseline (Visit 2) and after the 10th dose of VOR in Steps 2 and 3. If positive CMV testing results are available in the medical record, these results will be used for the baseline result. If the previous CMV IgG result in the medical record is negative, the test will be repeated at Visit 2. The 2nd and 3rd tests performed in the research lab will determine whether Vorinostat reactivates CMV enough to detect it in the plasma. The results will not be placed in the participant's medical record.

Epstein-Barr Virus (EBV) Viral Capsid Antigen (VCA) IgG Testing

We will perform EBV testing for research purposes only at baseline (Visit 2) and after the 10th dose of VOR in Step 2 or 3. If positive EBV testing results are available in the medical record, we will use these results for the baseline result. The 2nd and 3rd test performed in the research lab will determine whether Vorinostat reactivates EBV enough to detect it in the plasma. The results will not be placed in the participant's medical record

Vorinostat PK samples

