9.4.3 ANALYSIS OF THE OTHER ENDPOINT(S)

Other Activity Endpoints:

- **Change in the frequency of HIV infection per million resting CD4⁺T cells (RCI) from baseline to after treatment with VRC07-523LS and VOR**

We will analyze pre-VOR/VRC07-523LS and post- VOR/VRC07-523LS frequency of HIV infection per million resting CD4⁺T cells using a non-parametric 2-sided sign test (supplemented by longitudinal regression modeling to estimate the magnitude of changes) to determine whether or not a significant decrease of IUPM is observed. With 12 participants, there will be 80% power to reject H₀ (change expected with ART alone) in favor of H_A (greater change than expected with ART) if the true probability of observing a decrease in IUPM in a participant after VOR/VRC07-523LS is 0.93.

This is based on a 2-sided alpha = 0.05 and the assumption that observed HIV infection frequency would decrease with probability 0.54 on ART alone after 6 months without intervention, based on the decay of IUPM seen on ART alone [Crooks 2015, Siliciano 2003].

In addition to summarizing the number and proportion of participants who show decrease in IUPM after VOR/VRC07-523LS, we will describe the magnitude of the changes in decrease in IUPM after VOR/VRC07-523LS via the median fold-change and corresponding 95% confidence interval. We will also summarize the proportion of participants with >6-fold decreases; this magnitude change is rarely seen in participants on stable ART [9].

Other Endpoints: Activity

- **HIV-1 RNA by low level viremia assay measurement at baseline and after treatment with VRC07-523LS and VOR**

The virologic analysis will include estimation of the low level viremia levels at pre-treatment (screening and entry) and separately at post-treatment. We assume that the probability would be 0.10 (10%) for a baseline (pre-entry, entry) detectable low level viremia ≥ 1 copy. The assumption that 10% of participants with a quantifiable low level viremia at screening will have low level viremia assay below the limit of detection at a pre-treatment measure is an estimate based on data from A5244 in which 6 of 50 (12%) enrolled participants had undetectable low

level of viremia at pre-entry and 5 of 51 (10%) at entry after having a screening low level of viremia ≥ 1 copy (59).

Other Exploratory Analyses:

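### Does the reversed 10% assumption for baseline low-level viremia in section 9.4.3 affect any planned analysis?

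*Combined protocol and SAP*

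**What the plan says.** The synopsis (section 1.1) lists among the other, non-primary endpoints: "Change in HIV-1 RNA by low level viremia assay from baseline to post-treatment with VRC07-523LS and VOR". Section 3 puts the same endpoint in its tertiary/exploratory tier as "Change in HIV-1 RNA by SCA from baseline to post-VRC07-523LS/VOR", with the objective phrased as "viremia as measured by single copy assay (SCA) in participants who maintain suppression on ART".

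Section 9.4.3 plans to estimate levels before treatment and, separately, after it. It then adds: "We assume that the probability would be 0.10 (10%) for a baseline (pre-entry, entry) detectable low level viremia ≥ 1 copy". The next sentence explains the figure in the opposite direction: "The assumption that 10% of participants with a quantifiable low level viremia at screening will have low level viremia assay below the limit of detection". For support it cites A5244, where 6 of 50 (12%) were undetectable before entry and 5 of 51 (10%) were so at entry, all having had 1 copy or more when screened.

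Section 8.1 describes two baseline samples and makes this claim for the later ones: "2-4 low level viremia assay measurements after combination therapy with VOR and VRC07-523LS will allow a robust evaluation of changes in plasma levels". The Schedule of Events (section 1.3) places the assay at the enrollment visit, Day 0, Day 29, the pre-visit before Day 60, Day 89 and the evaluation visit.

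**The concern.** Consecutive sentences give opposite directions. One assigns 0.10 to a detectable baseline value. The other, offered as its basis, assigns about 10% to an undetectable one. The source rate is also conditional on at least 1 copy at screening. Sections 5.1 and 5.2 contain no such criterion; they require only a result below 50 copies/mL on a standard assay. Neither figure therefore describes the people enrolled here.

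If 0.10 were right, most participants would start below the limit and could not show a fall. Section 8.1 suggests that viremia might be reduced, so its promise of robustness would look unsupported. The two assay names could also leave it unclear what counts as detectable. At stake is what a reader may expect of this endpoint: almost nobody able to show a decrease, or almost everybody.

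**Working it through.** **Inputs.** From 9.4.3: 0.10 detectable as written; 6/50 and 5/51 undetectable in the source. From 9.2: up to 12 participants. From 8.1: two baseline samples.

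**The plan's own percentages.** 6/50 = 0.120 and 5/51 = 0.098, matching the stated 12% and 10%. Both are proportions undetectable. The complements are 0.880 and 0.902 detectable.

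**Could both sentences be true?** Their denominators differ: all participants against those quantifiable at screening. If 0.90 of those quantifiable at screening stay detectable, an overall 0.10 needs at most 0.10/0.90 = 0.11 quantifiable at screening. The plan says nothing of the kind and offers the second sentence as the basis of the first. Reversal is the natural reading.

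**Expected number of 12 with at least one detectable baseline value.** With per-sample probability p, the probability is p if the two samples are fully dependent and 1 − (1 − p)² if independent.

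| p | Basis | Probability | Expected of 12 |
|---|---|---|---|
| 0.10 | as written | 0.10 to 0.19 | 1.2 to 2.3 |
| 0.50 | assumed, for illustration | 0.50 to 0.75 | 6.0 to 9.0 |
| 0.880 | source, pre-entry | 0.880 to 0.986 | 10.6 to 11.8 |
| 0.902 | source, entry | 0.902 to 0.990 | 10.8 to 11.9 |

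At 0.10, the chance that none of 12 has a detectable baseline value is 0.9¹² = 0.28 (dependent) or 0.81¹² = 0.08 (independent).

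**Where the 0.10 is used.**
- Section 9.2 rests on the safety endpoint: with no events in 12, the one-sided 95% upper limit is 0.22. Low-level viremia plays no part.
- The only power statement in 9.4.3 is for IUPM, with probabilities 0.54 and 0.93. Low-level viremia plays no part.
- The viremia paragraph names no test, threshold or decision rule; it plans estimation.
- Under Other Exploratory Analyses, 9.4.3 says exploratory work has limited or no power, restricts analyses at 12 participants to descriptive summaries and within-participant comparisons, and plots individual data. Section 9.4.5 lists individual data by measure and time point.

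Replacing 0.10 with 0.90, or deleting it, alters no planned output.

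**Section 8.1.** Its claim rests on the number of measurements and refers to changes, not only decreases. Vorinostat is a latency reversal agent, and section 2.3.1 names detectable HIV RNA among its unknown effects. A participant undetectable at baseline can still show a rise.

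**Assay name.** The synopsis and section 3 state the same objective, one with low level viremia assay and the other with single copy assay, both in participants who stay suppressed on ART. Nothing points to two assays, and 9.4.3 gives a cut-off of 1 copy, though without a volume unit.

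**The case for a change.** The best case for a change is that the assumption is plainly misstated and cheap to correct: a few sentences, one assay name and its limit, no new samples or visits. Swapping the direction would not be enough, because the source rate applies to people selected for viremia. The endpoint is a change, yet the plan describes the two periods separately. A small table of detectable against below-limit counts, baseline against each later visit, would show who could have fallen and who rose.

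The reversal and the mismatch of populations stand. So does some tension with 8.1, since that section does expect a possible reduction and its word robust is generous for 12 people. It is not a contradiction: it arises only under the reading that the plan's own source undercuts, rises remain observable, and 9.4.3 itself urges caution. The table would rearrange values that are already to be plotted and listed; an analyst can produce it from the scheduled samples without any amendment, and no conclusion turns on it.

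**Conclusion.** The sentence in 9.4.3 has its direction reversed, and its source does not match this trial's participants. That is a clerical slip in background text for an exploratory endpoint. The literal reading implies 1.2 to 2.3 of 12 participants with a detectable baseline value and the source reading 10.6 to 11.9. The true share is not in the documents; it will be observed and reported rather than assumed. No sample size, power figure, test, threshold or safety conclusion depends on it, so no change to the plan is called for.

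This rests on two readings: that the viremia analysis stays descriptive, as 9.4.3 says for 12 participants, and that the two assay names mean one assay, as the matching objectives indicate.

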1 PROTOCOL SUMMARY

1.1 SYNOPSIS

Title: Phase I Study to Assess the Safety and Activity of Combination Therapy using a Novel Monoclonal Antibody, VRC07-523LS, and the Latency Reversal Agent, Vorinostat, to Reduce the Frequency of Latent, Resting CD4+ T Cell Infection in participants with HIV-1 infection suppressed on ART (The VOR-07 Study)

Study Description: Participants with HIV-1 Infection on ART with a CD4 T cell count ≥ 350 cells/mm³ and viral suppression for ≥ 24 months. Participants will receive two series of combination therapy consisting of one (1) intravenous (IV) dose of VRC-HIVMAB075-00-AB (VRC07-523LS) followed by 10 oral (PO) doses of Vorinostat (VOR) taken every 72 hours. Each series will last approximately 1 month and the two series will be separated by at least one month. Combination ART is (ART) maintained throughout the study.

Objectives:

Primary Objective:

1. To evaluate the safety and tolerability of combination therapy with VRC07-523LS and VOR in HIV-infected participants on ART.

Other Objectives:

1. Explore the effect of two cycles of VRC07-523LS and VOR on the frequency of latent, resting CD4+ T cell infection.
2. Explore the influence of VOR given with VRC07-523LS on low-level plasma viremia as measured by low level viremia assay in participants who maintain suppression on ART.
3. Compare HIV RNA expression within resting CD4+ T cells in HIV-infected participants on stable ART before and after combination therapy with VRC07-523LS and VOR measured at baseline (Step 1) and after the second series (Step 4).
4. Explore the impact of combined therapy with VRC07-523LS and VOR on the quantity of integrated proviral DNA quantification in T cell populations.
5. Characterize viral envelope sequences detected in plasma or cells that are not neutralized by VRC07-523LS from baseline to post-treatment with VRC07-523LS and VOR.
6. Evaluate the pharmacokinetics of VRC07-523LS combined with VOR and determine whether anti-drug antibody (ADA) to VRC07-523LS can be detected in recipients administered VRC07-523LS in combination with VOR.

Endpoints:

Primary Endpoint:

1. Safety: Occurrence of at least one \geq Grade 3 adverse event (AE) including signs/symptoms, lab toxicities, and/or clinical events that is possibly, probably, or definitely related to VOR or VRC07-523LS

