9.2 SAMPLE SIZE DETERMINATION

We will enroll up to 12 fully evaluable participants (who receive two cycles of VRC07-523LS and VOR) to examine the effect of adding VOR and VRC07-523LS to ART on persistent replication-competent HIV within resting CD4+ T cells.

Any participant who does not complete both series of VRC07-523LS and VOR and the leukapheresis in Step 4 for reasons other than a grade 3 or higher AE will be replaced, to ensure up to 12 evaluable participants for safety.

Since the trial will be stopped if two participants experience a study treatment-related toxicity of Grade 3 or higher, the criterion for safety is grade 3 or higher toxicity in no more than 1 of 12 participants in the study.

For n=12 participants, if there are no primary AEs, then the exact 95% 1-sided upper confidence limit (UCL) for the true AE rate will be 0.22. Thus, if no AEs are observed, one can confidently rule out event rates greater than 22%.

All other analyses are therefore equally exploratory.

Because a focus of the study is on safety and potential AEs, accrual will be staggered such that enrollment and treatment administration will include a maximum of 1 participant per week.

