- Following VOR/VRC07-523LS we will also explore whether there is a *depletion* of rc-RNA using the same statistical tests in the reverse (compare baseline rc-RNA to after two cycles of VOR/VRC07-523LS).
- To assess these within each individual participant (n of 1 analyses), we will use the non-parametric 2-sided Wilcoxon rank sum test to determine whether or not a statistically significant change in rc-RNA expression is observed, comparing rc-RNA levels measured in each of 24-36 replicate pools of 1 million resting CD4⁺ cells. Pools with undetectable RNA will be considered as 0 copies and analyzed as the lowest rank in this rank-based statistical test.

The pre-VOR rc-RNA expression will be determined as the median RNA copies over the individual pools of one million participant cells tested prior to VOR (setting undetectable RNA pools as 0 copies), and the post-VOR RNA expression level will be similarly determined. Changes in RNA expression will be evaluated by the exact sign test and the proportion of participants with increases versus decreases. Summaries of the magnitude of changes will be examined in terms of median fold-changes.

- We will also explore changes in the chromosomally integrated viral reservoir as measured by Q-PCR from baseline to post VOR/VRC07-523LS.
- We will also explore the change in frequency of viral envelope sequences detected in plasma or cells that are not recognized by VRC07-523LS from baseline to post VOR/VRC07-523LS.
- A 0.05 significance level will be used throughout, with no adjustment for multiple testing given the proof of concept nature of this study. Emphasis will be put on estimation with corresponding 95% confidence intervals to evaluate the scientific and biologic effect size. Individual-level data will be visualized in plots. Given the small sample size, exploratory analyses will have limited or no statistical power and findings should be interpreted with caution and assessed in a subsequent, larger study if the combined treatment is found to be safe and potentially efficacious. If the study is stopped at n=12 participants, statistical analyses will be limited to descriptive summaries and n of 1 analyses within each participant.

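### The n=12 sentence in Section 9.4.3 cancels, at full enrolment, the sign tests that the same section plans, and leaves only within-participant rank-sum tests that omit visit-to-visit variation

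*Combined protocol and SAP*

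**What the plan says.** All of the analysis text is in Section 9.4.3.

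- **Within-participant test.** "To assess these within each individual participant (n of 1 analyses), we will use the non-parametric 2-sided Wilcoxon rank sum test". The unit is the pool: the test works by "comparing rc-RNA levels measured in each of 24-36 replicate pools of 1 million resting" CD4 cells. Undetectable pools are scored 0 and share the lowest rank. The level is 0.05 throughout, without multiplicity adjustment.
- **Across-participant test on RNA.** "Changes in RNA expression will be evaluated by the exact sign test and the proportion of participants with increases versus decreases".
- **Across-participant test on IUPM.** A two-sided sign test with null probability 0.54 and alternative 0.93: "With 12 participants, there will be 80% power to reject" the null.
- **Rule at twelve.** "If the study is stopped at n=12 participants, statistical analyses will be limited to descriptive summaries and n of 1 analyses within each participant".

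Section 9.2 sets the sample size: "We will enroll up to 12 fully evaluable participants". Sections 1.1 and 3 place the RNA comparison between Step 1 and Step 4, and Section 3 ties it to leukapheresis #1 and leukapheresis #2. Section 8.1 confirms that there are only these two procedures. The abbreviation list does not define rc-RNA; I read it as HIV RNA in resting CD4 cells.

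**The concern.** The rule at twelve reads like a provision for an early stop, but the current text has no larger target. It therefore applies when the trial runs exactly as planned. Taken literally, it removes both sign tests, which use the participant as the unit, and keeps the tests that use the pool as the unit.

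All pools on one side of a rank-sum test are subsamples of a single collection. Their spread shows how precisely that collection was measured. It does not show how much the same participant's level would move between two visits without treatment. The test is valid for asking whether two collections differ. If its p-value is read as showing that the participant changed, a variance component is missing.

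At stake is what the trial can say about activity. A report that follows the rule could present participants with significant RNA changes as its only tested result, when some of those results may reflect ordinary differences between two visits.

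**Working it through.** **1. Is the IUPM test really a 12-participant test?** Inputs from Section 9.4.3: n = 12, null 0.54, alternative 0.93, two-sided 0.05 (0.025 per tail).

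- Upper tail under 0.54: P(X ≥ 11) = 0.0069; P(X ≥ 10) = 0.0363, which is above 0.025. The test rejects for a decrease at 11 or more.
- Power at 0.93: P(X ≥ 11) = 0.93^12 + 12 × 0.93^11 × 0.07 = 0.4186 + 0.3781 = 0.797.

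This reproduces the stated 80%. The plan powers a hypothesis test at n = 12 and also restricts n = 12 to description and within-participant tests. Both cannot stand.

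**2. What the rank-sum level covers.** Let m be the pools per collection, σ the pool SD, τ the visit SD and r = τ/σ. With no treatment effect, the difference between two collection means has variance 2(σ²/m + τ²). The pools show only 2σ²/m. The ratio is 1 + m·r², so the approximate error at a nominal 0.05 is

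2 × [1 − Φ(1.96 / √(1 + m·r²))].

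For r = 0.2:

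- m = 24: √1.96 = 1.40, 1.96/1.40 = 1.40, error 0.16.
- m = 36: √2.44 = 1.56, 1.96/1.56 = 1.25, error 0.21.

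More pools make the error larger. At r = 0 there is no inflation: without ties the exact size is 4.83% (24 v 24) and 4.90% (36 v 36).

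**3. Simulation of the rank-sum test itself.** The documents give neither τ/σ nor the share of undetectable pools, so both are assumed. Model: normal pools, one normal shift per collection, no treatment effect, undetectable pools tied at the lowest rank, tie-corrected two-sided test at 0.05. There were 100,000 participants per cell for 0% and 50% undetectable, and 40,000 for 90% and 95%. Entries are error in percent, 24 / 36 pools.

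| Undetectable | r = 0 | 0.05 | 0.1 | 0.2 | 0.5 |
|---|---|---|---|---|---|
| 0% | 4.7 / 5.0 | 5.5 / 5.7 | 7.3 / 8.7 | 14.9 / 19.9 | 43.7 / 52.1 |
| 50% | 4.9 / 4.9 | 5.2 / 5.6 | 7.0 / 8.1 | 13.3 / 17.5 | 39.7 / 48.1 |
| 90% | 4.5 / 5.1 | 4.6 / 5.4 | 5.2 / 6.3 | 7.4 / 10.4 | 19.1 / 27.8 |
| 95% | 1.9 / 3.6 | 2.0 / 3.8 | 2.3 / 4.4 | 3.1 / 6.3 | 9.8 / 15.7 |

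Repeat runs differ by a few tenths of a point. With 90-95% undetectable, several cells stay at or below 5% although visit-to-visit variation is present.

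**4. The tests that the rule would remove.** In a sign test each participant contributes one direction. Visit noise that is symmetric between the two visits does not raise its error above the nominal level.

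**The case against.** The strongest reply has four parts.

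- **These analyses are exploratory.** Section 9.2 says so. Section 9.4.3 stresses estimation with 95% confidence intervals, promises plots of individual data and urges caution. This stands and limits the consequence. But the caution is tied to small numbers and low power, which does not warn a reader about false positives from a missing variance component.
- **No decision rests on the within-participant p-values.** This also stands: the plan has no responder rule. The text does, however, use the test to declare a statistically significant change in that participant's expression, which invites the wider reading.
- **The rule at twelve is conditional, and the authors may want description only.** The documents do not show which text is intended. Description only would be consistent too, but the power statement and both sign tests would then have to go. As written, they conflict.
- **The inflation may be negligible.** It may. Nothing in the documents favours either end of the table. Section 8.1 recognises that baseline cell-associated RNA varies within a participant, but gives no size for it.

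Two stronger readings are tempting and are not supported. A reader might infer that any visit-to-visit variation takes the error above 5%; the sparse-detection rows show otherwise. A reader might also infer that the rank-sum tests would be the only inference left. They would be the only hypothesis tests on activity, because confidence intervals could survive as descriptive summaries.

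**Conclusion.** The contradiction is certain and rests on the text alone: at its planned maximum the trial is told both to run and not to run its across-participant sign tests.

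The error-rate point is sound in kind but unknown in size. For assumed SD ratios of 0.1, 0.2 and 0.5, the per-participant error is about 7-9%, 13-20% and 40-52% with 0-50% of pools undetectable, and about 2-7%, 3-11% and 10-28% with 90-95% undetectable. At a ratio of 0.05 or less the excess over 5% is under about 1 percentage point. These figures assume normal visit and pool variation and one collection per side. They describe the error of reading a significant result as a change in the participant. As a test of whether two collections differ, the rank-sum test is valid.

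The primary safety endpoint is not touched.

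**What to change.** Two wording changes in Section 9.4.3:

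1. Delete the n=12 sentence, or rewrite it to agree with Section 9.2 and with the power statement in 9.4.3, so that the participant-level sign tests already planned are the hypothesis tests at n = 12.
2. Add a statement such as: the within-participant rank-sum p-values compare the pools of two collections, do not account for visit-to-visit variation, and are reported descriptively, not as evidence that a participant changed because of treatment.

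No new samples, visits or assays are needed. The cost is that no individual participant can be called significantly changed on these p-values.

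### The planned rc-RNA fold-change is a ratio of medians that becomes exactly 0 once more than half the pools are negative, and no rule covers that case

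*Combined protocol and SAP*

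**What the plan says.** Section 9.4.3, under Other Exploratory Analyses, handles rc-RNA at two levels.

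- **Within a participant.** A two-sided Wilcoxon rank sum test compares "24-36 replicate pools of 1 million resting" CD4+ cells between time points. The rule for negatives is explicit: "Pools with undetectable RNA will be considered as 0 copies and analyzed as the lowest rank in this rank-based statistical test".
- **Across participants.** Each participant's pre-treatment level is the median number of copies over the pools, "setting undetectable RNA pools as 0 copies". The post-treatment level is formed in the same way. Then: "Changes in RNA expression will be evaluated by the exact sign test and the proportion of participants with increases versus decreases". For size: "Summaries of the magnitude of changes will be examined in terms of median fold-changes".

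The section sets no offset, no detection-limit substitution, no alternative summary, and no rule for a zero denominator or for two equal medians. Advancement to Step 2 (section 8.1) depends on the outgrowth assay (QVOA), not on rc-RNA, so nothing guarantees a non-zero baseline median.

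Section 9.2 sets the number of participants: "We will enroll up to 12 fully evaluable participants". Section 9.4.3 adds that if the study stops at 12, analyses are restricted to descriptive summaries and single-participant analyses.

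**The concern.** Coding an undetectable pool as 0 is harmless in a rank test, because only its position matters. It is not harmless when the zeros enter a median that then becomes the numerator or denominator of a ratio. Once negatives are the majority, the median no longer responds to how many pools are positive or how much RNA they hold. Three outcomes follow:

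- **Baseline 0:** the fold-change has no finite value.
- **Both 0:** the fold-change is 0/0 and the sign test sees a tie, whatever happened among the positive pools.
- **Only the follow-up 0:** the ratio is 0. The direction is recorded correctly, but a moderate fall and complete loss of RNA look the same.

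Section 9.4.3 puts its emphasis on estimating effect size, and the fold-change is the planned estimate for this endpoint. If the rule for zeros is chosen only after the data are seen, that choice can shape the result.

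**Working it through.** The plan states no power, rate or detection fraction for rc-RNA, so there is no figure of its own to reproduce. The check takes the pool count (24 to 36) from section 9.4.3. The fraction *p* of pools that are positive is an **assumption**, shown over a range.

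**Step 1: when the median is 0.** For an even number *N* of pools, the median is 0 when fewer than *N*/2 are positive. With 24 pools, 11 positives give 0, and 12 positives give half the smallest positive value. With 36 pools, 17 positives give 0 and 18 do not.

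**Step 2: how often.** P(median = 0) = P(Binomial(*N*, *p*) ≤ *N*/2 − 1), treating pools as independent:

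| Positive pools (assumed) | N = 24 | N = 30 | N = 36 |
|---|---|---|---|
| 30% | 0.969 | 0.983 | 0.991 |
| 40% | 0.787 | 0.825 | 0.854 |
| 50% | 0.419 | 0.428 | 0.434 |
| 60% | 0.114 | 0.097 | 0.083 |
| 70% | 0.012 | 0.006 | 0.004 |

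With 24 pools and 12 participants who share one value of *p*, the chance of at least one zero baseline median is 1 − (1 − 0.0115)^12 = 0.13 at 70% positive and 1 − (1 − 0.1143)^12 = 0.77 at 60%.

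**Step 3: the ratio post/pre for each pattern.** Zero over zero is undefined, positive over zero is infinite, and zero over positive is 0 (its logarithm and the fold-decrease are not finite).

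**Step 4: a good baseline with a moderate fall.** Assume Poisson copies per pool and single-copy detection, so that *p* = 1 − e^(−λ).

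- Baseline 80% positive: λ = −ln 0.2 = 1.609. A 3-fold fall gives λ = 0.536 and *p* = 0.415. P(follow-up median = 0) is 0.74 with 24 pools and 0.81 with 36.
- Baseline 70% positive: λ = 1.204. A 2-fold fall gives λ = 0.602 and *p* = 0.452. P(follow-up median = 0) is 0.61 and 0.66.

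So a 2- to 3-fold fall would often be reported as a ratio of 0.

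**Step 5: an invented example of the tie.** Take 24 pools. Before treatment, 10 are positive (10, 12, 15, 20, 25, 30, 40, 50, 60 and 80 copies; total 342). After treatment, 4 are positive (10, 12, 15 and 20; total 57). The means are 342/24 = 14.25 and 57/24 = 2.375, a 6-fold fall, and the rank sum p-value is 0.03. Both medians are 0, so the planned fold-change is 0/0 and the sign test counts a tie.

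**The case against.** The case for leaving the plan alone has real weight.

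- **Depletion acts on the follow-up.** A reader might infer that the fold-change becomes undefined just where a treatment effect would appear. The documents do not support that. A positive baseline with a zero follow-up gives a defined ratio of 0 and is counted as a decrease. An undefined ratio needs a zero baseline, which treatment does not cause. What depletion costs is the size of the fall. This stands.
- **Little inference is at risk.** A reader might also infer that every affected pair shrinks a test on 12 participants. With enrolment capped at 12 and section 9.4.3 limiting a study stopped at 12 to descriptive and single-participant analyses, the across-participant sign test may not be run. The retained test is the rank sum test, where zeros have a rule. It would have many ties but is not undefined, and it detects the change in the example above. This largely stands, although the fold-change is itself a descriptive summary and so remains.
- **A median across participants tolerates some extremes.** Values of 0 or infinity can still be ranked; only 0/0 pairs need a rule. This stands.
- **Frequency is unknown.** With 70% or more of pools positive at both time points, zero medians are rare. This stands.
- **The failure would be visible.** Individual data are to be plotted (section 9.4.3) and listed (section 9.4.5), and all non-safety analyses are called exploratory (section 9.2). This limits the harm but supplies no estimate.
- **The median resists one extreme pool.** That is a fair reason to keep it, but as a companion rather than the only basis for a ratio.

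**Conclusion.** The point holds as a minor one. As written, the participant-level summary is 0 whenever more than half the pools are negative, and section 9.4.3 has no rule for the fold-change or the tie that results. The exposure is the exploratory descriptive fold-change, plus the across-participant sign test if it is run. The primary safety endpoint, the QVOA analysis and the within-participant rank test are untouched.

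The size cannot be fixed from the documents. Zero medians are the usual result at 40% positive or below, close to an even chance at 50%, and rare at 70% or above. These figures assume independent pools with a common positive fraction. The statement that a 2- to 3-fold fall can look like complete loss also assumes Poisson counts and single-copy detection.

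**What to change.** Amend section 9.4.3 as follows:

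1. Report participant-level rc-RNA as total copies divided by total cells assayed, that is, mean copies per million over all pools. Base fold-changes on this value and show the planned median alongside.
2. Report the proportion of positive pools before and after treatment.
3. Where the total is 0, report the fold-change as a bound using a stated limit. One choice is the one-sided 95% Poisson limit, −ln 0.05 ≈ 3.0 copies over the cells assayed: 3.0/24 ≈ 0.125 copies per million with 24 pools, or 3.0/36 ≈ 0.083 with 36. This assumes single-copy detection; otherwise use the assay's own detection limit. One copy is too low for this purpose, being only a 63% limit (1 − e^(−1)). If both totals are 0, report the pair as not estimable.
4. State how equal values are treated in the sign test, if it is run.
5. Keep zeros as the lowest rank for the rank sum test.

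The cost is wording: the pool-level data are already collected. The drawback is that a mean is more sensitive to a single high pool, so show the pool-level plot with it.
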